3.2 Participants

Inclusion (all of the following)

- Age \geq 18 years old
- New admission to the medical or transplant ICU at Memorial Hermann Hospital in Houston
- ICU admission hemoglobin level of at least 7 g/dL. The ICU admission hemoglobin will be the most recent hemoglobin value available at the time of screening for inclusion in the study.
- Randomization is expected within 12 hour of admission to the ICU

Exclusion (any of the following)

Conditions that affect the generation or loss of RBCs

- Clinical bleeding. Defined as menstrual bleeding, bleeding leading to a change in the frequency of hemoglobin monitoring or to an order for a medication, transfusion, procedure, or consultation intended to prevent or treat bleeding.
- Known hemolytic disorder (e.g. sickle cell disease, hereditary spherocytosis, autoimmune hemolytic anemia)
- Bone marrow disorder (e.g. aplastic anemia, marrow infiltration disorder, chemotherapy within the last 8 weeks)

Randomization to adult size phlebotomy tubes is not recommended

- Jehovah's Witnesses

Collection of blood tests is not possible or desired

- Patient is comfort care measures only

Inability to complete the desired time of follow up

- Refractory shock: mean arterial blood pressure below 60 mmHg despite maximal doses of 3 vasopressors. Maximal dose of vasopressors are as follows: Norepinephrine 70 mcg/min; vasopressin 0.04 units/min; epinephrine 35 mcg/min; dopamine 20 mcg/kg/min; phenylephrine 350 mcg/min
- Severe acidosis: pH below 7 in more than one arterial blood gas within 24 hours of ICU admission in the absence of diabetic ketoacidosis

Other

- Surgical admission diagnosis
- Pregnancy
- Current prisoner

33 Allocation

All patients admitted to the medical or transplant ICU will be screened for eligibility. Group assignment will be done using the randomization module in the Research electronic data capture (RedCap). Randomization will be stratified by ICU admission hemoglobin level (7 to 9.49 g/dL, 9.5 to 11.99 g/dL, and 12 g/dL or greater). Patients will be randomized using permuted blocks of 4 or 6 and a 1 to 1 ratio, into one of two groups: the pediatric size phlebotomy tubes group or the adult size phlebotomy tubes group.

34 Interventions

Pre-intervention period (1 month)

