The first objective of this period is to standardize the pediatric tubes phlebotomy process. Study procedures will be presented to the ICU nurses by email, printed material, and lectures. Information will include the type of pediatric tube and the blood volume needed for each test, and the importance to collect only the total estimated blood volume according to the tests that need to be performed. Pocket size cards that include the suggested volume of blood to be drawn for each pediatric tube will be provided. No guidance regarding the phlebotomy process when using adult size tubes will be given so that it reflects usual practice. The volume of fluid

drawn to clear the intravenous line will be returned to the patient in a sterile fashion in both groups whenever possible. The frequency and type of blood tests performed will follow usual practice.

The second objective of the pre-intervention period is to provide RBC transfusions recommendations to the ICU physicians. This will be accomplished by email and during any of the regular Critical Care Division meetings. An RBC transfusion will be recommended if the hemoglobin is less than 7 g/dL or if there is bleeding with associated hemodynamic instability regardless of the hemoglobin level. It will be dependent upon the ICU physician to make the final determination regarding the need of any transfusions.

Intervention period (5-11 months)

Blood tests will be collected using pediatric and adult phlebotomy tubes in the experimental and control groups, respectively (Table 1). Arterial blood gases, blood cultures, and lactate levels will be collected using the same tubes in both groups. The exposure period will be from randomization until the hemoglobin is less than 7 g/dL, an RBC transfusion order is placed, the patient is discharged from the ICU (time of an acceptance note) or dies (time of death), clinical bleeding or surgery occur, comfort care measures only are initiated, or the patient stays in the ICU for more than 30 consecutive days.

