3.5 Outcomes

Primary

The primary outcome will be the time from randomization to hemoglobin less than 7 g/dL or RBC transfusion order.

Secondary

The main secondary outcome will be the rate of change in hemoglobin (g/dL/patient/day) in the ICU. This will be calculated as the most recent hemoglobin prior to randomization minus the last hemoglobin prior to ICU discharge, death, RBC transfusion, clinical bleeding, surgery, or change of clinical status to comfort measures, divided by the number of days (rounded to the nearest 0.5) between these two values (crude estimate). If the longitudinal measures of hemoglobin levels deviate substantially from a linear trajectory, we will use a growth model to capture the best fitting function of time (see Analysis Plan for details) and generate a predicted rate of change.

Other secondary outcomes will be the proportion of participants receiving an RBC transfusion while in the ICU, the proportion of patients with at least one inadequate blood sample for laboratory analysis, and the ICU mortality. An inadequate blood sample is defined as any blood sample that requires recollection.

The patient's admission height and weight will be used to estimate the total blood volume of each patient based on Nadler's equation.¹¹ The total daily phlebotomy volume per participant will be calculated based on the number of blood tests per patient per day and the minimal blood volume for analysis of each test.

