3.7 Analysis plan

Baseline variables (e.g. gender, race, age) between groups will be examined for clinically significant differences that may have occurred by chance. If a clinically significant difference is noted, both unadjusted and adjusted analyses will be performed.

Intent-to-treat analyses will be used. The primary outcome will be assessed using time to event analysis with the Cox proportional hazard model including treatment group and ICU admission hemoglobin level group (stratifying variable). Censoring events will be death, ICU discharge, clinical bleeding, surgery, initiation of comfort care measures, and end of the study. We will report the hazard ratio and 95% confidence interval (CI).

We will assess whether the longitudinal measures of hemoglobin follow a linear trajectory. If they substantially deviate, we will employ multilevel mixed models including a quadratic term for time or splines to capture the non-linear change while accounting for within-subject correlation. We will generate predicted rates of change to compare between the study groups.

To compare the rate of change in hemoglobin (either crude or predicted) between the two study groups, a linear regression model will be used with treatment and ICU admission hemoglobin groups as covariates. Multiple regression analysis will be used to assess the relationship between the rate of change in hemoglobin as the dependent variable, and age, admission hemoglobin, acute physiology and chronic health evaluation (APACHE) II score, acute or chronic renal disease, sepsis admission diagnosis, use of medications that can cause bleeding, intervention group, and ICU admission hemoglobin group as independent variables. Proportions of RBC transfusion and proportions of at least one inadequate blood sample will be compared among the two groups using logistic regression models with treatment group and ICU admission hemoglobin level group as covariates.

Sample Size

It is estimated that the primary outcome will occur in about 20-40% of the participants in the control group.^{1,2,6,12-14} A total of 200 patients (100 in each group) will be randomized in the study. This number of participants was chosen to allow completion of the study in a reasonable time frame while obtaining preliminary information to estimate an unbiased treatment effect. This sample size allows a reasonable width of the 95% CI for the rate of the primary outcome in each group (+/- 8%).

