4. DATA AND SAFETY MONITORING

The adverse events related to the use of pediatric phlebotomy tubes are not expected to be different than the ones that occur with adult tubes. Potential events include local complications at the site of blood collection, complications related to blood loss including anemia and RBC transfusions, and insufficient blood for analysis requiring recollection of blood. Previous studies in adults have not shown a difference in the number of insufficient samples between patients using adult or pediatric size tubes.^{15,16}

Participants that receive the other group's intervention will remain in their assigned group for the duration of the trial. These protocol deviations as well as instances of inadequate blood samples will be recorded in the blood tests record forms by the investigators (Appendix).

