7. DATA COLLECTION AND DATABASE MANAGEMENT

6.1 Data collection

The investigators will fill out the blood tests form to document the number of blood tests performed and the occurrence of insufficient samples or crossover between interventions. This will be done through review of the electronic medical record and interview of the nurses. This information and data obtained from the patient's electronic medical record will be entered directly in the RedCap database, a secure electronic database (Appendix).

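### The inadequate-sample outcome pools assigned-tube samples with samples drawn in the same tubes in both arms, and no assigned-tube comparison is planned, so a true excess of failed pediatric-tube samples would be diluted by an unknown amount

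*Combined protocol and SAP*

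**What the plan says.** Section 3.5 lists, among the other secondary outcomes, "the proportion of patients with at least one inadequate blood sample for laboratory analysis". It then gives the definition: "An inadequate blood sample is defined as any blood sample that requires recollection". No tube, test or cause is excluded.

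Section 3.4 says of the intervention period: "Arterial blood gases, blood cultures, and lactate levels will be collected using the same tubes in both groups". Those samples are therefore not exposed to the randomized difference in tube size.

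Section 3.7 gives the analysis: "Proportions of RBC transfusion and proportions of at least one inadequate blood sample will be compared among the two groups using logistic regression models". The covariates are study arm and the stratum of admission hemoglobin. The section contains no analysis by tube type.

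Section 4 names "insufficient blood for analysis requiring recollection of blood" among the potential adverse events. Section 6.1 has the investigators "document the number of blood tests performed and the occurrence of insufficient samples or crossover between interventions". Table 1, which lists the tubes, and the Appendix form are not in the text available for this review.

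**The concern.** The outcome is the only named one that could show pediatric tubes failing more often than adult tubes. The others are the primary composite, hemoglobin decline, transfusion and ICU mortality. It therefore informs the feasibility objective in section 2.2 and bears on the remark in section 4 that earlier adult studies found no difference in insufficient samples.

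As defined, one redrawn blood gas makes the patient a case whatever happened to the assigned tubes. If such redraws are about as common in both arms, they raise both proportions and reduce the contrast. A diluted contrast points toward the result that section 4 already anticipates, and it would be carried into the design of the larger trial that this pilot is meant to inform.

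**Working it through.** **Inputs from the plan.** The outcome is at least one recollected sample, yes or no, per patient (3.5). Three sample types use common tubes (3.4). Size: "A total of 200 patients (100 in each group) will be randomized in the study". Allocation: "permuted blocks of 4 or 6 and a 1 to 1 ratio" (3.3). The plan gives no expected rate, power or precision for this outcome, so there is no planned figure to reproduce. The ±8% in section 3.7 concerns the primary outcome and plays no part here.

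**Assumptions, not in the plan.** Samples fail independently. Same-tube failures are equally likely in both arms. Power is for a two-sided 5% comparison of two proportions with 100 per arm (pooled variance under the null). Sample counts and failure rates are illustrative.

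**Step 1. Formula.** Let p0 and p1 be the probabilities of at least one failed assigned-tube sample (adult, pediatric), and b the probability of at least one same-tube recollection. The counted proportion is

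q = 1 − (1 − p)(1 − b),

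so q1 − q0 = (1 − b)(p1 − p0). With a = 1/(1 − p) and c = 1/(1 − b), the odds ratio is (a1·c − 1)/(a0·c − 1). This falls as b rises whenever p1 > p0, and stays above (1 − p0)/(1 − p1). If p1 = p0, it is 1 for every b.

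**Step 2. Assigned tubes only.** With 25 samples at 1% and 2%:

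- p0 = 1 − 0.99^25 = 22.2%
- p1 = 1 − 0.98^25 = 39.7%
- Difference 17.4 points; odds ratio (0.397/0.603)/(0.222/0.778) = 2.30; power about 76%

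**Step 3. Add same-tube samples**, with b = 1 − (1 − failure rate)^number:

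| Same-tube samples | b | Counted, adult vs pediatric | Difference (points) | OR | Power |
|---|---|---|---|---|---|
| none | 0% | 22.2% vs 39.7% | 17.4 | 2.30 | 76% |
| 10 at 0.2% | 2.0% | 23.8% vs 40.8% | 17.1 | 2.22 | 74% |
| 5 at 0.5% | 2.5% | 24.1% vs 41.1% | 17.0 | 2.20 | 73% |
| 10 at 1% | 9.6% | 29.7% vs 45.4% | 15.8 | 1.97 | 64% |
| 15 at 1% | 14.0% | 33.1% vs 48.1% | 15.0 | 1.87 | 58% |
| 25 at 1% | 22.2% | 39.5% vs 53.1% | 13.6 | 1.73 | 49% |
| 15 at 2% | 26.1% | 42.6% vs 55.4% | 12.9 | 1.68 | 44% |

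**Step 4. Other patient-level rates.** Assume p0 = 10% and p1 = 25%. The odds ratio is 3.00 (power 80%) at b = 0, 2.69 (76%) at b = 2%, 2.05 (59%) at b = 10% and 1.71 (43%) at b = 20%. The difference falls from 15.0 to 12.0 points over that range. With p0 = 5% and p1 = 15%, the odds ratio falls from 3.35 (66%) at b = 0 to 1.81 (37%) at b = 10%. Rarer assigned-tube failures make the relative dilution worse.

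**Step 5. What equality contributes.** Take the row with b = 9.6% and let b differ by arm. The undiluted 17.4-point difference returns if (1 − p1)(1 − b1) = (1 − p0)(1 − b0) − 0.174. That is 0.603 × (1 − b1) = 0.778 × 0.904 − 0.174 = 0.529, so b1 is about 12.3%. A modest excess of same-tube recollections in the pediatric arm would cancel the dilution in the difference.

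**The case against.** The strongest reply is that the intervention is more than a tube. Section 3.4 has nurses taught to limit the total draw to the volume the ordered tests require when pediatric tubes are used, and gives no guidance for adult tubes. A tight total draw could leave a blood gas or lactate short. The all-sample count would then capture a real consequence of the strategy, and the assumption of equal same-tube failure would be wrong. The documents do not say whether this happens. The argument stands far enough to rule out two tempting conclusions: that same-tube samples should be dropped from the outcome, and that they form a clean negative control.

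Second, every rate and count above is assumed. With few same-tube samples and low failure rates the loss is slight, and on the absolute scale it is smaller still: 17.4 to 15.8 points with 10 samples at 1%. Section 3.7 sets no power target for this outcome in a pilot. This also stands. Power serves here only as a yardstick for dilution.

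Third, the wording may be narrower in practice. Sections 4 and 6.1 speak of insufficient rather than inadequate samples, so whether a contaminated culture counts is arguable. Neither section excludes same-tube samples, however, and a blood gas or lactate that is too small meets either term.

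Finally, a restricted analysis may already be possible. The phlebotomy-volume calculation in section 3.5 uses a minimum volume for each test, so test type must be available. But no restricted analysis is specified, and one chosen after seeing the data would be post hoc.

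**Conclusion.** The concern holds for direction, not for size. The definition in section 3.5 mixes samples that can carry a tube effect with samples drawn in identical tubes, and section 3.7 does not separate them. If same-tube recollections are about equal across arms and independent of assigned-tube failures, a true pediatric excess is attenuated by (1 − b) on the difference scale and by more on the odds-ratio scale. In the main scenario the odds ratio falls from 2.30 to between 2.22 and 1.68, depending on inputs the plan does not give.

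A reader might infer that the trial is bound to report falsely that pediatric tubes are safe. The documents do not support that. The protocol calls this a secondary outcome, not a safety outcome, although section 4 lists the event as a potential adverse one. Equal same-tube failure is not assured. And where there is no true excess, equal background recollection leaves the odds ratio at 1. This is an inexpensive improvement to a lower-tier outcome, not a flaw in the primary analysis.

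**What to change.** - In sections 3.5 and 3.7, pre-specify the tube comparison as the proportion of patients with at least one recollected sample among samples drawn in the study-assigned tubes (Table 1), using the logistic model already planned.
- Keep the all-sample proportion as a measure of total recollection burden.
- Report same-tube recollections by arm, noting that the limited total draw in the pediatric arm could affect them too.
- Record the test or tube type for each recollection, if the Appendix form does not already do so, and use one term for the event throughout.

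The cost is one more reported line and possibly one form field. Sample size and primary analysis are unchanged.

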3.6 Blinding

The primary outcome assessors will be blinded to the intervention assignments. Study participants, nurses, and physicians will not be blinded.

3.7 Analysis plan

Baseline variables (e.g. gender, race, age) between groups will be examined for clinically significant differences that may have occurred by chance. If a clinically significant difference is noted, both unadjusted and adjusted analyses will be performed.

Intent-to-treat analyses will be used. The primary outcome will be assessed using time to event analysis with the Cox proportional hazard model including treatment group and ICU admission hemoglobin level group (stratifying variable). Censoring events will be death, ICU discharge, clinical bleeding, surgery, initiation of comfort care measures, and end of the study. We will report the hazard ratio and 95% confidence interval (CI).

We will assess whether the longitudinal measures of hemoglobin follow a linear trajectory. If they substantially deviate, we will employ multilevel mixed models including a quadratic term for time or splines to capture the non-linear change while accounting for within-subject correlation. We will generate predicted rates of change to compare between the study groups.

To compare the rate of change in hemoglobin (either crude or predicted) between the two study groups, a linear regression model will be used with treatment and ICU admission hemoglobin groups as covariates. Multiple regression analysis will be used to assess the relationship between the rate of change in hemoglobin as the dependent variable, and age, admission hemoglobin, acute physiology and chronic health evaluation (APACHE) II score, acute or chronic renal disease, sepsis admission diagnosis, use of medications that can cause bleeding, intervention group, and ICU admission hemoglobin group as independent variables. Proportions of RBC transfusion and proportions of at least one inadequate blood sample will be compared among the two groups using logistic regression models with treatment group and ICU admission hemoglobin level group as covariates.

Sample Size

It is estimated that the primary outcome will occur in about 20-40% of the participants in the control group.^{1,2,6,12-14} A total of 200 patients (100 in each group) will be randomized in the study. This number of participants was chosen to allow completion of the study in a reasonable time frame while obtaining preliminary information to estimate an unbiased treatment effect. This sample size allows a reasonable width of the 95% CI for the rate of the primary outcome in each group (+/- 8%).

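### The primary Cox model uses admission hemoglobin only in three bands, so chance imbalance inside the band that starts at the 7 g/dL event threshold is left unadjusted (low severity, cheap to fix)

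*Combined protocol and SAP*

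**What the plan says.** Section 3.7 sets the primary analysis as a "Cox proportional hazard model including treatment group and ICU admission hemoglobin level group (stratifying variable". No continuous hemoglobin term is listed. The bands come from the Allocation section (3.3): "Randomization will be stratified by ICU admission hemoglobin level (7 to 9.49 g/dL, 9.5 to 11.99 g/dL, and 12 g/dL or greater".

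The numeric value exists for everyone, because it decides eligibility and stratum. Section 3.2: "The ICU admission hemoglobin will be the most recent hemoglobin value available at the time of screening for inclusion in the study".

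The endpoint is tied to the floor of the lowest band. Section 3.5: "The primary outcome will be the time from randomization to hemoglobin less than 7 g/dL or RBC transfusion order".

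The numeric value is used once in section 3.7, in the multiple regression of predictors of hemoglobin change, whose covariates include "age, admission hemoglobin, acute physiology and chronic health evaluation (APACHE) II score" as well as the band. The between-group comparison of hemoglobin change and the logistic models for transfusion and inadequate samples use treatment and band only. Section 3.7 also provides for adjusted analyses if a baseline difference is judged clinically important. It gives gender, race and age as examples and sets no threshold.

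**The concern.** A patient admitted at 7.2 g/dL needs a fall of just over 0.2 g/dL to have the event; one admitted at 9.4 needs a fall of more than 2.4. The band model treats them as equally at risk. Blocked randomization within bands equalizes the number of patients per arm in each band, but not where they sit inside it. If by chance one arm's lowest-band patients start somewhat closer to 7, the hazard ratio shifts for a reason unrelated to the tubes, and the planned model cannot remove the shift.

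This matters because section 2.1 makes estimating the effect size the primary objective, and a later trial may be designed around this one estimate.

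**Working it through.** **The plan's own figure.** The plan states no hazard ratio, power or event target. Its one precision figure is a half-width of 8 points for the event rate in each group of 100. The formula 1.96 × √(p(1−p)/100) gives 7.8 points at p = 0.20, 9.0 at 0.30 and 9.6 at 0.40, so the figure reproduces at the low end of the planned range. It concerns event rates and does not bear on the choice of covariates.

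**Inputs from the documents.** 200 patients, 1:1; lowest band 7 to 9.49 g/dL; event threshold 7 g/dL; "the primary outcome will occur in about 20-40% of the participants in the control group".

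**Inputs assumed, because the documents give none.** Share of patients in the lowest band 20-50%; values uniform within that band; hazard ratio g per 1 g/dL lower hemoglobin of 1.25 to 3.

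**Step 1: ordinary chance imbalance in the lowest band.** SD within the band = 2.49/√12 = 0.72 g/dL. SE of the between-arm difference in means = 0.72 × √(2/n per arm).

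**Step 2: shift in the hazard ratio inside that band for a one-SE imbalance** = g^SE − 1.

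| Share in band | n per arm | SE, g/dL | g = 1.25 | g = 1.5 | g = 2 | g = 3 |
|---|---|---|---|---|---|---|
| 20% | 20 | 0.227 | 5.2% | 9.7% | 17.1% | 28.4% |
| 30% | 30 | 0.186 | 4.2% | 7.8% | 13.7% | 22.6% |
| 40% | 40 | 0.161 | 3.7% | 6.7% | 11.8% | 19.3% |
| 50% | 50 | 0.144 | 3.3% | 6.0% | 10.5% | 17.1% |

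**Step 3: whole-trial hazard ratio, proportional-hazards simulation.** 600 trials for each of 15 settings, treatment hazard ratio 0.7, mean ICU censoring time 6 days capped at 30. The Cox model with bands was compared with one using linear hemoglobin in their place. The last column divides the SD of the difference between the two log hazard ratios by the banded model's SE.

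| g | One-SD shift | Median absolute shift | Chance of a shift above 12% | Events in lowest band | Shift / SE |
|---|---|---|---|---|---|
| 1.25 | 4-5% | 2-3% | 1-3% | 37-55% | 0.13-0.16 |
| 1.5 | 7-8% | 4-5% | 8-12% | 43-62% | 0.21-0.27 |
| 2 | 11-14% | 8-9% | 28-36% | 51-72% | 0.38-0.43 |
| 2.5 | 13-19% | 9-11% | 37-48% | 55-79% | 0.49-0.52 |
| 3 | 16-24% | 12-14% | 50-57% | 59-82% | 0.61-0.63 |

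The linear model was correctly specified here, which favours adjustment.

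**Step 4: modelling the event as crossing 7 g/dL.** Three sets of simulations with no tube effect used assumed decline, measurement noise and length of stay; event rates ran from 13% to 31%. A one-SD imbalance in the lowest band multiplied the banded hazard ratio by 0.83-0.91, a shift of 9-17%. With the numeric value added, the factor was 0.90-0.98. In one set the gradient inside the band was 2.7-5.9 per g/dL.

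**Step 5: scale against sampling error.** With no tube effect, 20-40% of 200 gives 40-80 events. SE(log HR) ≈ 2/√events = 0.32 to 0.22, so the 95% confidence interval extends by a factor of 1.9 to 1.6 either side.

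**Step 6: what adjustment changes.** In the step 3 runs:
- The empirical SD of the banded log hazard ratio was 0.95 to 1.09 times its model-based SE, with Monte Carlo error of about 3% (1/√1200). The planned interval therefore already reflects the imbalance.
- The SD of the estimate did not fall consistently after adjustment (for example 0.294 banded against 0.296 adjusted).
- The adjusted log hazard ratio lay further from zero by about 0.01-0.04 at g = 2 to 2.5, and by up to about 0.07 at g = 3.

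In the threshold-crossing runs:
- Power rose 2-6 points before and 0-4 points after calibration for size in one set, and about 4-5 points before calibration in another.
- Type I error of the adjusted test was about 4.5-7% with the robust SE. One set gave 6-9% with the model-based SE.

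**The case against.** The strongest reply is that the planned analysis is valid as it stands. Adjusting for the stratifying factor follows the randomization, and the plan does so in every treatment comparison for which it names covariates. Within-band imbalance is random in sign and averages out, and steps 5 and 6 show that the interval allows for it. The net gain is small, while adjustment changes the estimand slightly and can make the test a little liberal. All of this stands, and it is why the point is minor.

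The provision for adjusted analyses after a notable baseline difference is also a real safeguard, and its list of examples is open. But it is data-driven and has no threshold. Whether a difference of about 0.2 g/dL would trigger it cannot be determined from the plan, so it does not reliably replace prespecification.

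A reader might infer four stronger things that the documents do not support:

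- *The primary estimate is biased or its interval too narrow.* The only systematic effect seen was the slight attenuation in step 6.
- *The hazard ratio will move by a set amount, such as 12-15%.* That needs a gradient of about 2-2.5 per g/dL and roughly a one-SD imbalance; the plan states neither.
- *Most events arise in the lowest band.* The plan gives no event shares. The simulated share is 37-55% at the weakest gradient and passes half in every setting only from g = 2.
- *The plan contradicts itself by using the numeric value for hemoglobin change.* It does so only in the predictor regression, not in the between-group comparison.

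In the other direction, the weakest gradient is hard to credit for a threshold endpoint. It gives the patient at 7.2 only 1.25^2.2 = 1.6 times the hazard of the patient at 9.4.

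**Conclusion.** The point holds as a low-severity improvement to the primary analysis. The plan discards known prognostic information in the band where distance from the threshold should matter most, and stratification does not make up for it. The 4-24% range covers gradients of 1.25 to 3 per g/dL, and 9-17% applies when events are generated by crossing 7 g/dL. In 10 of the 15 proportional-hazards settings the one-SD shift was below half a standard error; at a gradient of 3 it was about 0.6.

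These sizes depend on assumed gradients, hemoglobin distribution, decline, noise and stay. The threshold-crossing runs did not reach the upper part of the planned 20-40% event range. The case rests on removing a measured source of chance error from this trial's estimate, not on validity or a large power gain.

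**What to change.** In section 3.7, prespecify continuous ICU admission hemoglobin as a covariate beside the stratifying group in the primary Cox model, with a robust (sandwich) standard error. Do the same in the logistic model for RBC transfusion. Report the band-only Cox model as a supportive analysis. State that the covariate is the screening value that sets the stratum, since section 3.5 defines its baseline as the last value before randomization, which could be a later measurement.

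The cost is a sentence or two of SAP text and no new data. The hazard ratio becomes more conditional and lies slightly further from 1, its SD should not be expected to fall, and the test may be slightly liberal even with the robust standard error. The plan should acknowledge these when the result is used to design a later trial.

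### Does the missing rule for an RBC order that is itself the first sign of clinical bleeding (event or censored?) need to be written into the primary analysis?

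*Combined protocol and SAP*

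**What the plan says.** Section 3.5 defines the primary outcome as "the time from randomization to hemoglobin less than 7 g/dL or RBC transfusion order", with no exception for the reason behind the order.

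Section 3.7 lists the reasons for censoring: "Censoring events will be death, ICU discharge, clinical bleeding, surgery, initiation of comfort care measures, and end of the study".

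Clinical bleeding is defined once, in the exclusion criteria of 3.2, under the group headed "Conditions that affect the generation or loss of RBCs". Apart from menstrual bleeding, it means bleeding that leads to closer hemoglobin monitoring or to "an order for a medication, transfusion, procedure, or consultation intended to prevent or treat bleeding". Section 3.7 reuses the term without restating the definition.

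Section 3.4 expects some RBC orders to be placed for bleeding, since one of its two transfusion recommendations is for "bleeding with associated hemodynamic instability regardless of the hemoglobin level". It then lists the ends of exposure without ranking them: "The exposure period will be from randomization until the hemoglobin is less than 7 g/dL, an RBC transfusion order is placed", followed by "the patient is discharged from the ICU (time of an acceptance note) or dies (time of death), clinical bleeding or surgery occur". Discharge and death have a stated time; clinical bleeding does not.

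Sections 3.6 and 5 provide for blinded outcome assessment. Under section 5, one blinded investigator decides when each participant has completed the study and whether the primary outcome occurred.

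**The concern.** Read together, 3.5, 3.7 and the definition in 3.2 can give one act two opposite codes. Take a patient who starts to bleed and whose first documented response is an RBC order. Under 3.5 that order is an event. Under 3.7 the patient has clinical bleeding and is censored. A Cox model needs one status per patient, and the software's handling of ties between patients does not supply it.

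Estimating the effect size on RBC transfusions is the pilot's primary objective (2.1), and a single hazard ratio carries it. If bleeding-driven orders count, the ratio includes transfusions that smaller tubes may not influence. If they are censored, it concerns the remaining orders and hemoglobin falls. Two analysts with the same data could report different ratios, each claiming to follow the plan. The undated onset of bleeding also seems to leave open which hemoglobin is the last one in the main secondary outcome, which uses "the last hemoglobin prior to ICU discharge, death, RBC transfusion, clinical bleeding, surgery, or change of clinical status to comfort measures".

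**Working it through.** **Who is affected**

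| Situation | Code under the plan |
|---|---|
| Hemoglobin below 7 g/dL before any bleeding act | Event |
| RBC order with no bleeding | Event |
| Earlier qualifying act (closer monitoring, medication, procedure or consultation order), RBC order later | Censored at the earlier act |
| RBC order for bleeding is the first qualifying act, or coincides with it | Open |

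Only the last row is open. A hemoglobin below 7 g/dL that coincides with the first bleeding act is a similar tie. Patients with clinical bleeding at entry are already excluded, as are those with hemolytic or marrow disorders and surgical admissions.

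**The plan's own figures.** Section 3.7 gives a control event rate of 20-40%, 100 patients per group, and a 95% CI half-width of 8 points for the event rate. The half-width is 1.96 × sqrt(p(1 − p)/100): 7.84 points at p = 0.20, which matches, and 9.60 at p = 0.40.

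**Assumptions, none from the documents.** Let s be the share of control events that are tied orders, from 0.05 to 0.30. The hazard ratio is 0.70 for all other events and 1.00 for tied orders.

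**Control events that change code, per 100 patients**
- 20% rate: 20 × 0.05 = 1 to 20 × 0.30 = 6
- 40% rate: 40 × 0.05 = 2 to 40 × 0.30 = 12

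**Hazard ratio if tied orders are counted:** 0.70 × (1 − s) + 1.00 × s
- s = 0.05: 0.715
- s = 0.30: 0.79
- If they are censored: 0.70

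**Precision if they are censored.** With no ties, pediatric-arm events at a hazard ratio of 0.70 are 100 × (1 − 0.80^0.70) = 14.5, or 100 × (1 − 0.60^0.70) = 30.1. Multiply the events in both arms by (1 − s). At s = 0.30:
- 20% rate: 14 and 10.1 events; SE of the log hazard ratio = sqrt(1/14 + 1/10.1) = 0.413; 95% CI 0.31-1.57
- 40% rate: 28 and 21.0 events; SE = sqrt(1/28 + 1/21.0) = 0.289; 95% CI 0.40-1.23

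**Shift in standard errors**
- s = 0.05: ln(0.715/0.70) = 0.0212. Divided by 0.354 (20% rate) this is 0.06; divided by 0.248 (40% rate) it is 0.09.
- s = 0.30: ln(0.79/0.70) = 0.121. Divided by 0.413 this is 0.29; divided by 0.289 it is 0.42.

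**Same data coded both ways.** In 4,000 simulated trials per setting (100 per arm, exponential times, discharge as the only other censoring, unstratified Cox model), the two hazard ratios differed by these factors, in either direction:

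| Control rate | s | Median | 90th percentile |
|---|---|---|---|
| 20% | 0.05 | 1.06 | 1.17 |
| 20% | 0.30 | about 1.20 | 1.60 |
| 40% | 0.05 | 1.04 | 1.12 |
| 40% | 0.30 | 1.15 | about 1.4 |

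These factors mix the systematic shift (at s = 0.30, 0.79/0.70 = 1.13) with chance from a handful of events. Even the 90th percentiles at s = 0.30 lie inside the corresponding confidence limits: 1.57/0.70 = 2.24 and 1.23/0.70 = 1.76. With no tied orders the difference is zero.

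**The secondary outcome.** RBC transfusion and clinical bleeding are both cut-offs for the last hemoglobin. In a tie, either code leaves essentially the same value. Only dating bleeding from its onset rather than from the act could alter it, and then only if a hemoglobin was drawn in between.

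**The case for a change.** The strongest case for a change is that the fix is cheap and the quantity affected is the trial's main result. The protocol foresees RBC orders for bleeding, so the tie is not far-fetched. The definition in 3.2 is an entry criterion and is not expressly carried into follow-up. Blinding keeps the coding even between arms, but it does not say what the hazard ratio measures or let an outsider reproduce it. At the far end of the illustration (40% rate, s = 0.30), 12 control patients per 100 change code, more than the 9.60-point half-width for an arm's event rate, so the raw event count could look quite different under the two codes.

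Most of this is fair as description. The gap exists, and a sentence on dating and ties would make the plan tidier. It does not show that an analyst following the plan would reach an unsound result. Each code gives a coherent hazard ratio: one for all RBC orders or low hemoglobin, the other for those not presenting as bleeding. The text leans towards censoring: the bleeding leads to the order and so precedes it, and bleeding is treated throughout as a reason to stop follow-up. The large count in the extreme case rests on an assumed share with no support in the documents, and the hazard ratio there still moves by less than half a standard error. The proportion receiving an RBC transfusion in the ICU is a separate outcome in 3.5, worded without regard to the reason for transfusion, so such orders are not hidden under either code.

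**Conclusion.** The concern describes a true but small gap: no tie rule when an RBC order for bleeding is the first or simultaneous act that defines clinical bleeding. It does not call for a change to the plan. A workable reading exists, one blinded investigator can apply it to both arms, and writing it down would only record whichever code the investigators already use. Any harm is to reproducibility rather than a bias between arms, and the usual report of how events and censoring were coded would meet it.

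On the illustrative figures the choice moves the hazard ratio from 0.70 to between 0.715 and 0.79 (0.06-0.42 standard errors). With 30% of events censored as ties, the 95% CI is already about 0.31-1.57 at a 20% control rate and 0.40-1.23 at 40%. These sizes rest on the assumed 5-30% share, a hazard ratio of 0.70 for other events and no tube effect on bleeding orders. The true share is unknown and may be close to zero. The conclusion also assumes that the blinded investigator uses one consistent practice throughout; case-by-case coding would weaken it.
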